In the experimental sessions, the SCAs will approach and distribute souvenirs (e.g. a pen) or leaflets to the smokers at outdoor smoking hotspots for 3-4 hours. The souvenirs and leaflets will have SC messages, quitline number and other SC services. If a smoker is willing to accept them and talk to the SCAs, the SCAs will advise the smoker to quit using the AWARD protocol. The AWARD protocol includes (1) Ask the smoking history, (2) Warn about the high risk (i.e., half of the smokers will die of smoking-related diseases), (3) Advise to quit, (4) Refer to the SC clinics of TWGHs and (5) Repeat the above advice (Do-it-again) [4]. Our previous studies have shown that the AWARD protocol is a feasible and appropriate tool used by non-healthcare professionals to promote smoking cessation [4-6]. If the smoker is interested in using the SC services, the SCAs will introduce NRT to the smoker and conduct a preliminary assessment of his/her eligibility for enrolling in the "NRT sampling" programme. The SCAs will invite him/her to go to the smoking cessation

truck nearby to receive counselling by an onsite nurse. If the smoker is not eligible, he/she can still enroll in the cessation service provided by the SC clinics.

11. Intervention: NRT sampling and medication counselling

In the experimental sessions, an onsite nurse will assess whether each participant is fit for using NRT with further assessment on his/her current physical status, medication and blood pressure. If the participant is willing to use NRT to quit smoking and pass the nurse's assessment, he/she will be prescribed the NRT sample, regardless of whether they use NRT for smoking reduction and when the quit day is. The nurse will help the participant decide which type of NRT product (gum: 2mg, patch: 14mg or 21mg) that he/she can use and advise him/her on how to use the NRT based on his/her smoking habit and daily cigarette consumption. In addition, the nurse will deliver medication counselling which addresses five main components: (1) the benefits for using NRT in quitting, (2) withdrawal symptoms due to smoking cessation, (3) side effects of NRT, (4) instructions for using NRT, and (5) making appointments for TWGHs SC clinics. Afterwards, the participant will receive 1-week free NRT and an instruction card about the use of NRT.

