15.1.1.4 Participants who have contra-indication(s) to NRT

If the smoker tells the nurse that he/she has contra-indication(s) to NRT, the nurse will advise him/her to stop using NRT to avoid risks.

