15.1.1.5 Participants who continue smoking during the use of NRT

If the smoker has a dual use of cigarettes and NRT, the nurse will advise him/her to stop using NRT to avoid overdose.

15.1.2 Participants who receive NRT samples and whose quit day is more than one week after baseline

The research assistant will contact the participants around one week after baseline. The participants will receive motivational messages to encourage them to quit and enroll in the

SC clinics if they have not. They will also be asked if they need to contact the TWGHs counsellors for early cessation support. Otherwise, the participants will be contacted by the TWGHs nurse around one week after their quit day as outlined above in section 15.1.1.

15.1.3 Participants who do not receive NRT samples but make an intake appointment within one week after baseline

A TWGHs nurse will contact the participants within one week after baseline reminding them to attend the intake session. The nurse may contact some participants via phone for provision of further counselling or encouragement if necessary.

15.1.4 Participants who do not receive NRT samples but make an intake appointment more than one week after baseline

The research assistant will contact the participants around one week after baseline. The participants will receive motivational messages to encourage them to quit. They will also be asked if they need to contact the TWGHs counsellors for early cessation support. The participants will receive reminder message from the TWGHs nurse before their intake appointment.

15.1.5 Participants who do not receive NRT samples and do not make an intake appointment

The participants will receive motivational messages from the research assistant around one week after baseline to encourage them to quit and enroll in one of the SC clinics.

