To compare the two primary quitting outcomes (binary) between experimental and control group, generalized estimating equations model will be used. Other secondary outcomes will be analyzed with either generalized estimating equations models (binary outcomes; e.g. tobacco abstinence) or linear mixed model (continuous outcomes; e.g. perceived importance to quit smoking).

Cost analysis will be conducted to assess if the intervention is cost-effective, as what we did in our published paper [5]. Direct operating costs included salary (of training personnel, research assistants and SCAs), recruitment, telephone follow-up and publicity items. The total operation costs for the experimental group will include the cost for NRT sampling. Costs for study design, venues for training (provided by HKU), analysis, report writing and

irrelevant administration were excluded. In each group, the cost per successfully recruiting a smoker to receive any SC service was calculated by dividing the total cost by the number of smokers who report use of any smoking cessation. Similarly, the costs per quit attempt will also be calculated.

19. Time-line:

	2018						2019												2020						
	7	8	9	10	11	12	1	2	3	4	5	6	7	8	9	10	11	12	1	2	3	4	5	6	
HCPS – NRT sampling																									
Development of the intervention, instruments and protocol																									
Site selection																									
Recruitment of ambassadors																									
Training for staff, ambassadors and nurses																									
Subject recruitments																									
3-day / 1-month follow-up																									
3-month follow-up																									
6-month follow-up (+validation)																									
6-month follow-up for SCAs																									
Data entry and cleaning																									
Data analysis																									
Report preparation																									

20. Describe any unusual or discomforting procedures to be used: Nil.

21. Are there any hazards associated with the investigation? No.

22. Ethical and legal issues

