According to the Drug Database of the Drug Office under Department of Health (http://www.drugoffice.gov.hk/eps/do/en/consumer/search_drug_database.html), all NRT products (in all forms and dosages) are classified as Part 2 Poisons and are referred as over-the-counter medicines. All Part 2 Poisons are regulated by the Pharmacy and Poisons Ordinance (Cap. 138). Accordingly, Part 2 Poisons can be sold in a pharmacy (ASP) or a medicine (LSP). They can also be supplied for the purpose of medical treatment by a person, who is not necessarily a medical practitioner, who practices medicine in a clinic registered in the Medical Clinics Ordinance.

The present proposal targets to deliver a 1-week of free NRT to the smokers at the outdoor smoking hotspots, so that the smokers can obtain and use them as soon as being motivated to quit. To fully comply with the Ordinance, our collaborator (Tung Wah Group of Hospitals) has already registered a license from the Pharmacy and Poisons Board for their smoking cessation truck, which can park nearby the outdoor hotspots, so that our registered nurses can legitimately prescribe NRT to the recently-recruited smokers in this truck. The truck is a mobile clinic which can provide brief counseling sessions and medications like a clinic. The student ambassadors will mainly be responsible to approach the smokers at the hotspots and invite them to receive advice and NRT in the truck.

Other measures will also be undertaken to protect the participants: (1) Our intervention will include a brief advice about how to correctly use the NRT, side effects and other safety measures. Hence, our intervention is even safer than smokers buying over-the-counter NRT from pharmacy without any advice. (2) Only registered nurses will be responsible to provide NRT to the participants. (3) All on-site documentations will be locked in a cabinet of the truck, and handled carefully by the project coordinators. We will strictly follow the data security guideline under the University of Hong Kong. (4)

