Participants who do not meet the inclusion criteria will be suggested to meet the physicians in the smoking cessation clinics and obtain the medication advice from the physicians before using NRT. They will not be included in this trial. This will help ineligible participants to use NRT safely. (5) The pilot study of the present proposal was fully reviewed and approved by the Institutional Review Board (IRB) of the University of Hong Kong / Hospital Authority Hong Kong West Cluster (Ref: UW 15-232). Therefore, our procedures and interventions met the ethical requirement and protect participants' privacy. We have already submitted the IRB application for the present study. The recruitment will only start when the research is approved by the IRB.

23. Direct access to source data/documents

The raw data will be stored in the CD-ROM and locked in a cupboard with keys kept by the Principal Investigator. Only the Investigators and Research Assistant of the project will be permitted to access to raw data and/or study record. The data will be kept for 10 years or longer after the study completed.

24. Dissemination of study result

The research findings will be disseminated through publication in international peer reviewed journals including American Journal of Health Promotion and Nicotine & Tobacco Research. Papers will also be presented in international conferences such as (1) the Annual Scientific Meeting of the Society on Research on Nicotine and Tobacco (SRNT); national conferences such as (2) the Asia Pacific Conference on Tobacco or Health and Cross-strait Conference on Tobacco Control (China, Hong Kong, Macau and Taiwan); and (3) regional conferences in Mainland China and Hong Kong.

25. Consent

Eligible participants will be invited to participate in the study by obtaining written consent.

26. Conflict of interest: None

27. Financing and insurance

This research is funded by Health and Medical Research Fund of the Food and Health Bureau.

28. References

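### Section 21 declares no hazards although the protocol itself names several, and no side-effect or serious-event outcome is planned in either arm

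*Combined protocol and SAP*

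**What the plan says.** Section 21 is a single line: "Are there any hazards associated with the investigation? No".

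Other sections of the same document treat NRT as carrying risk:

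- Section 9 excludes people with certain cardiac conditions or a recent cardiac event, and women who are pregnant or breastfeeding. It also provides for blood pressure checks.
- Section 11 requires an onsite nurse to assess fitness for NRT before supply. Side effects are part of the counselling ("3) side effects of NRT, (4) instructions for using NRT").
- Section 15.1.1.4: "If the smoker tells the nurse that he/she has contra-indication(s) to NRT, the nurse will advise him/her to stop using NRT to avoid risks".
- Section 15.1.1.5, on people who go on smoking while using NRT: "the nurse will advise him/her to stop using NRT to avoid overdose".
- Section 22 lists advice on side effects among its protective measures, then concludes that "our intervention is even safer than smokers buying over-the-counter NRT from pharmacy without any advice". Under item (4), people found ineligible "will be suggested to meet the physicians in the smoking cessation clinics and obtain the medication advice from the physicians before using NRT".

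Section 5 gives training outcomes, process outcomes, two primary quitting outcomes and six secondary ones. None is a side effect or serious event. Section 18 analyses none, and no procedure for recording or reporting adverse events is described. Past-month NRT use is a secondary outcome at 1 and 3 months, collected by blinded interviewers in both arms.

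**The concern.** A protocol that screens for a hazard, counsels on it and gives advice to avoid it cannot also state that there is none. An ethics committee or reader who relies on Section 21 is misinformed by the protocol's own account.

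The larger consequence is for the data. NRT supply is the intervention, yet the plan provides for no harms rate in either arm. The nurse's question in Section 15.1.1 is neither an outcome nor analysed, and it reaches only people who took a sample. Under Section 15.1.2, sample holders with a later quit day are first contacted by a research assistant and reach the nurse about a week after that day. Controls are advised to obtain free NRT from the clinics (Section 11), so some will use it. Section 15.2 gives them reminders, motivational messages and, for some, a counselling call, but no systematic question about problems with NRT. Nurse notes could therefore not be compared between arms, and data that were never collected cannot be recovered at analysis.

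**Working it through.** **Plan's own figure.** The documents state no safety figure. The sample size is reproduced only because it gives the smaller count of people supplied.

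- Inputs (Section 17): quit attempts 20% versus 8%, two-sided 5% level, 95% power, ratio 2:1.
- Pooled proportion = (0.08 + 2 × 0.20)/3 = 0.16.
- Controls = [1.960 × √(1.5 × 0.16 × 0.84) + 1.645 × √(0.08 × 0.92 + 0.20 × 0.80/2)]² / 0.12² = (0.880 + 0.645)² / 0.0144 ≈ 161.4.
- Total = 3 × 161.4 ≈ 484.3, which rounds up to the stated 485. Rounding within arms gives 162 + 324 = 486.
- Design effect = 1 + (8 − 1) × 0.1 = 1.7, and 1.7 × 485 = 824.5, so 825 as stated.

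**People supplied with NRT.** The target in Section 16 is 720. At the stated minimum, the experimental arm is 825 × 2/3 = 550. This is an upper figure for recipients, because Sections 15.1.3 to 15.1.5 provide for experimental participants without a sample.

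**What a harms item could show.** With zero events among n people, the one-sided 95% upper limit p solves (1 − p)ⁿ = 0.05, so p ≈ 3/n.

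| Group | n | 3/n |
|---|---|---|
| Recipients, target | 720 | 0.42% |
| Recipients, minimum | 550 | 0.55% |
| Users at 34%, target | 0.34 × 720 ≈ 245 | 1.2% |
| Users at 34%, minimum | 0.34 × 550 = 187 | 1.6% |

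The exact limits for recipients are 0.415% and 0.543%. The 34% is the pilot's NRT use at 3 months (Section 7); carrying it over is an assumption.

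**Sensitivity to loss.** If only 70% were followed (assumed), the limits become 3/504 = 0.60% and 3/385 = 0.78% among recipients, and 3/171.5 ≈ 1.7% and 3/130.9 ≈ 2.3% among users.

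**Chance of seeing at least one event**, 1 − (1 − p)ⁿ, at assumed true rates:

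- 0.1%: 51% (n = 720) or 42% (n = 550)
- 0.5%: 97% or 94%
- 1%: over 99% in both

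As written, the plan provides for none of these statements.

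**The case against.** The strongest reply is that the plan is not careless about safety. It has exclusion criteria, a nurse's assessment before supply, counselling on side effects, supply by registered nurses only, and physician advice for ineligible smokers. The nurse also actively asks sample holders about trouble using NRT. All of that stands: the gap is in measuring and reporting harms, not in precautions.

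A reader might go further in four ways that the documents do not support.

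- *That a harms item would test the safety claim in Section 22.* It would not. The comparator in that sentence is over-the-counter purchase without advice, and neither arm is that. Controls receive the same procedures without the sample and instruction card. The sentence is also an ethics rationale, not one of the objectives in Section 4.
- *That participants are never asked about side effects.* The questionnaire is not in the documents, and nurses may phone some controls. What is established is that no such outcome is listed or analysed and no systematic enquiry is described for controls.
- *That Sections 15.1.1.4 and 22(4) prescribe conflicting actions for the same person.* The first concerns enrolled people who already hold NRT. The second concerns people outside the trial who have not yet used it, and its criteria extend to residency, age and language. Stop advice does not rule out a physician. How the two routes relate is unexplained, which calls for clarification only.
- *That participants are told nothing about risk.* Consent pages were removed from the text, so this cannot be judged.

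A comparison between arms among NRT users would also be thin. The pilot's 2% control use gives about 0.02 × 360 ≈ 7 people. Clinic referral could raise this to 72 if every control service user in the Section 16 target took NRT and none obtained it elsewhere. The harms report should therefore be descriptive.

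**Conclusion.** The point holds in two parts. Section 21 is contradicted by Sections 9, 11, 15.1.1.4, 15.1.1.5 and 22. Separately, the trial supplies NRT to as many as 550 to 720 people with no harms rate planned for either arm. With a recorded item and zero serious events, the report could give an upper limit of about 0.42% to 0.55% among recipients, or 1.2% to 1.6% among users. These limits assume full follow-up, independent participants, every experimental participant at the minimum size receiving a sample, and, for users, the pilot's 34%. Losses, clustering by session or fewer recipients would widen them.

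This should be changed, but it does not threaten the primary efficacy comparison. It does not show that the intervention is unsafe or that screening is inadequate.

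**What to change.** 1. Reconcile Section 21 with Sections 9, 11, 15.1.1.4, 15.1.1.5 and 22 by naming the hazards that the protocol already lists.
2. Add a prespecified side-effect and serious-event item to the blinded 1- and 3-month interviews in both arms, after the primary-outcome and NRT-use items. List it in Section 5 and report it descriptively in Section 18, by arm and by NRT use.
3. Soften the comparative safety sentence in Section 22 or support it with evidence.
4. Have the sponsor clarify how the action in Section 15.1.1.4 relates to the physician route in Section 22(4). No clinical rule is proposed here.

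The cost is one or two questions in existing calls, plus protocol wording. Calls become slightly longer, and an interviewer who hears NRT details at one call may be partly unblinded at later ones. Placing the item last protects only the primary outcomes at the same call.

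The document carries the same date as the planned study completion. If the interviews have ended, items 1, 3 and 4 still apply, and the report should state that harms were not systematically collected, if that is so.
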